1.0 Background

The management of immature non-vital teeth following trauma or pulpal infection secondary to caries or dental anomalies e.g. fractured dens evaginatus tubercles is a challenge for dentists. Traditionally, the treatment prescribed for immature non-vital teeth is to thoroughly disinfect the root canal system and perform apexification procedures using materials such as Ca(OH)_2 or Mineral Trioxide Aggregate (MTA), followed by filling the root canal with gutta-percha. This technique however does not produce increased thickness of dentine or gain in root length to the immature tooth. Furthermore, in a retrospective study by Cvek, the risk of cervical root fractures has been found to be markedly higher in immature teeth treated with Ca(OH)_2 apexification and gutta percha, and its frequency was related to the stage of root development (1). This is possibly attributed to the fact that long term placement of calcium hydroxide as an intracanal medicament can induce brittleness of the tooth structure due to its hygroscopic & proteolytic properties, thus rendering them prone to root fracture (2). This emphasizes the importance of seeking other treatment approaches. More biologically compatible options, which offer regenerative possibilities and continued development of tooth structure have been explored, but are largely reported only in case reports and cases series.

Pulp tissue in immature teeth has the potential for regeneration following pulpal damage because they have wide open apices that are rich in blood supply and potentially viable apical tissues. Given non-infectious conditions, Regenerative Endodontic Therapy (RET) includes treatments such as revascularization via blood clotting technique, postnatal stem cell therapy, pulp and scaffold implantation, injectable scaffold delivery, three-dimensional cell printing, and gene delivery(3). All have the potential to provide revolution in endodontic therapy as it offers patients an alternative method to save teeth that have compromised structural integrity and poor long-term prognosis. Revascularization via blood clotting aside, the other RET techniques mentioned are designed on the accepted principles of tissue engineering, and aim to harness the potential of stem cells in the apical papilla through the provision of a sterile environment, signaling molecules and a scaffold within the root canal of the non-vital tooth (4). However, the use of advanced tissue engineering techniques for dental tissue regeneration, although promising, is still only at a laboratory and animal trial stage(4).

The advantages of RET in young patients include better long term prognosis of teeth due to continued root development and thickening of lateral dentinal walls; possible occupancy of root canal systems by vital tissues; and shorter treatment time with potential reduction in treatment fatigue. Case reports on revascularization via blood clotting technique (5-9) have shown that immature non-vital teeth can demonstrate continued root development under favourable conditions, which promote healing of apical

pulp tissue. Other case series (6, 8, 10) showed similar outcomes of continued maturation of root apices in teeth which had previously developed extensive periradicular lesions with sinus tract formation prior to treatment. It is essential to note that in some of these cases, mechanical instrumentation was not employed, and disinfection of the root canal was achieved purely through chemical means of disinfection using irrigation with sodium hypochlorite and application of antibiotic pastes.

These findings demonstrate that vital pulp rich in regenerative potential is present at the most apical portion of the root, and that immature non-vital teeth with periradicular pathology can still undergo apexogenesis in the presence of a generated sterile environment. Findings also indicate a paradigm shift of endodontic treatment away from predominantly restorative philosophy with filling of available canal spaces towards a biological and regenerative approach.

Status of scientific evidence on RET

As of current status, most of the evidence present on RET remain at case report and case series levels. While the multitude of publications to date appear to suggest that RET can lead to positive outcomes (e.g. healing of apical periodontitis, continued radiographic root development, and improved tooth survival), the success of this technique should still be taken with caution since case reports/series in nature are predisposed to publication bias with primarily positive outcomes reported. According to the American Association of Endodontists statement on regenerative procedures (11), there are currently no evidence based guidelines to support a standardized protocol, which provides the most favorable outcome in the treatment of infected immature permanent teeth. Various groups have in the course of their work made modifications to the procedures reported in the literature.

There are currently only two randomized controlled trials currently published in the literature. (12, 13) Nagy et al compared radiographic healing of apical periodontitis following MTA apexification versus RET procedures, in which the triple antibiotic paste was used as the intra-appointment medicament. They found that RET procedure allowed the continued root development in necrotic teeth with evidence of healing in some but not all cases, suggesting that healing outcomes using RET method has yet to be consistent or predictable.(13) Nagata et al found that although the outcomes of patients with traumatized teeth treated with triple antibiotic pastes vs combination of calcium hydroxide and 2% chlorhexidine gel had similar clinical and radiographic outcomes, only 5 teeth (41.7%) and 3 teeth (27.3%) respectively demonstrated an increase in root length.(12) On the whole, the sample sizes in both these studies were very small at 12 patients per group, and the clinical outcomes and success rates shown were not convincing of the benefit of this treatment protocol. There is without doubt a paucity in well documented long term prospective clinical studies to show evidence on the success and survival rates of

teeth treated with RET, with many aspects surrounding the predictability of this procedure and true nature of treatment outcomes remaining unanswered.

Various intra-canal medicaments have been reported for use as root canal disinfectants with successful clinical outcomes. The feasibility is supported by controlled animal studies and case reports, in which the combination of ciprofloxacin-metronidazole-minocycline (14), or “3-Mix” paste as it is commonly known, at present is most well documented to be effective in disinfecting immature teeth with apical periodontitis and inducing apical closure in these infected teeth. However, a known drawback is discolouration of the tooth likely to be due to the minocycline component of the antibiotic mixture (15). To circumvent this problem, other combinations of intracanal medicaments for root canal disinfection have been proposed and reported in the literature. These include Ca(OH)_2 (16, 17) and different combinations of antibiotics preparations (18, 19), all which show comparable clinical success rates to the 3-Mix preparations. Having said that, the quest for an intracanal medicament with the most reliable clinical outcome is still underway.

This also begs the question if antibiotics are truly a necessary and beneficial component in the preparation for a sterile root canal. Prior laboratory in-vitro studies have determined that disinfection protocols have a profound effect on stem cells of the apical papilla (SCAP) as well as dentine microhardness. Yassen et al demonstrated that dentine microhardness was significantly reduced when triple or double antibiotic mixtures were used for treatment of dentine compared to Ca(OH)_2 (20). Antibiotic paste formulations used in RET procedures were found to be directly toxic to stem cells even at concentrations as low as 1% of doses currently used in treating patients, while conversely dentin conditioning with Ca(OH)_2 was found to promote SCAP survival and proliferation (21, 22). This may well have clinical implications impacting fracture resistance and SCAP survival in immature permanent teeth with already compromised root thickness.

Given that this procedure (Regenerative Endodontic Therapy using revascularization via blood clotting method) has been carried out in children in Singapore since 2007, and a retrospective study is in progress, it is considered timely to conduct a prospective randomized controlled study to evaluate the need for antibiotic pastes and the outcome and success of RET.

2.0 Research questions/Aims and Objectives:

Research questions:

1. Are there differences between treatment outcomes of a 2-Mix antibiotic paste (Ciprofloxacin and Metronidazole) vs disinfection with the currently accepted multiple-visit protocol in non-surgical root canal treatment (i.e. disinfection with NaOCl solution followed by Ca(OH)₂ as inter-appointment dressing) with respect to:
 - i. Resolution of apical periodontitis.
 - ii. Thickening of dentinal walls and/or continued root development with or without apical closure.
2. Which are the baseline characteristics which could predispose a case to successful outcome?
3. Will discolouration of teeth occur and to what extent?

Primary aim

1. To assess frequency of periapical healing in the two sets of experimental protocols.
2. To study the differences in qualitative and quantitative increase in root dimensions of different protocols, by evaluating continued root development and thickening of dentinal walls.

Secondary aims

1. To evaluate if tooth discolouration occurs by evaluating the changes in tooth colour following treatment using the different protocols.
2. To evaluate patient reported outcomes, including oral health-related quality of life (OHRQL), inter-appointment symptoms, and satisfaction ratings.

Hypothesis:

1. There is no difference between treatment outcomes of RET using 2-Mix antibiotics (Ciprofloxacin and Metronidazole) vs disinfection with the currently accepted multiple-visit protocol in non-surgical root canal treatment for RET procedures in non-vital immature permanent teeth in children.
2. There is no difference between patient related outcomes of RET using 2-Mix antibiotics (Ciprofloxacin and Metronidazole) vs disinfection with the currently accepted multiple-visit protocol in non-surgical root canal treatment for RET procedures in non-vital immature permanent teeth in children.

3.0 Materials and Methods

3.1 Study Design

This will be a multi-center, parallel-group allocation (1:1), randomized controlled trial of treatment carried out on non-vital immature permanent teeth in children using revascularization via blood clotting technique. Both the patient and the assessors will be blinded to the intervention. The clinical study will be carried out at the School Dental Service, Health Promotion Board and NUH Dental Centre over a period of 3 years.

Regenerative Endodontic Therapy (using revascularization via blood clotting method) will be defined as any permanent tooth which has undergone at least a two-stage procedure involving:

- a. Disinfection using sodium hypochlorite irrigation and placement of inter-appointment dressing (antibiotics or calcium hydroxide), followed by
- b. Procedures which involve inducing bleeding and blood clot and hence intentional initiation of proliferation of stem cells of the apical papilla (SCAP) into the root canal.

3.2 Intervention: Study arms and Investigational Product (IP) used

Following canal debridement procedures, patients will be randomly assigned to receive different combinations of inter-appointment dressing, which will be one of the following:

- Experimental: Group A - Double Antibiotic Paste consisting of Ciprofloxacin and Metronidazole
Intervention named: 2-Mix Antibiotic Paste
- Experimental: Group B - Non-setting calcium hydroxide paste inter-appointment dressing, aimed at prevention of re-colonization of canal space.
Intervention named: Ca(OH)₂

3.2.1 Preparation of Antibiotics

Group 1 - 2-Mix Antibiotic Paste: This will be prepared at a 1:1 ratio of Ciprofloxacin 500mg (Tablet) and Metronidazole (Tablet) 400mg. To be crushed in a pill crusher immediately prior to administration. The antibiotic powder will be mixed with 3-4 drops of sterile water, to consistency of MTA/wet pumice.

Group 2 - Ca(OH)₂: This will be Ca(OH)₂ paste placed into the root canal according to currently employed procedures.

3.3 Outcome measures

The study will evaluate the following clinical outcomes following this procedure:

- i. Resolution and healing of periapical radiolucency
- ii. Measurements of thickening of dentinal walls and/or continued root development with or without apical closure
- iii. Discolouration of tooth
- iv. Patient reported outcomes, including oral health-related quality of life (OHRQL), symptoms, and satisfaction ratings.

3.4. Participants

3.4.1 Inclusion and Exclusion criteria

The inclusion criteria are as follows:

1. Patients aged 6-16 years of age
2. Patients who are fit and healthy or with ASA 1 or ASA 2 medical conditions
3. Patients with cooperation level that would allow treatment under local analgesia, application of rubber dam isolation and taking of intraoral radiographs.
4. Patients with permanent premolars that have incomplete root formation with an open apex of greater than 1mm width as observed radiographically and of single root canal morphology (23)
5. Patients with single rooted immature permanent teeth having one of the following pulpal and periapical diagnosis:
 - a. Pulpal
 - i. Necrotic pulp
 - ii. Symptomatic and inflamed pulp not expected to heal. During attempted Cvek or cervical pulpotomy procedures, if the pulpal bleeding does not stop with direct pressure within 5 minutes, pulpectomy will be carried out and the patient will be recruited for RET procedures.
 - b. Periapical
 - i. Symptomatic apical periodontitis (with or without a radiographic apical lesion)
 - ii. Asymptomatic apical periodontitis (with a radiographic apical lesion)
 - iii. Acute apical abscess
 - iv. Chronic apical abscess

Teeth will be deemed non-vital if either are non-responsive to sensibility tests (i.e. EPT and cold tests), and/or present with signs and symptoms of non-vitality (e.g. swelling and abscess).

The exclusion criteria are as follows:

1. Patients aged > 16 years of age.
2. Patient with known allergies to Ciprofloxacin (or any fluoroquinolones class of antibiotics) or Metronidazole antibiotics.
3. Patients with medical conditions and/or receiving medications that would affect:
 - a. Their body's ability to heal e.g. Diabetes; or
 - b. Their ability to clot efficiently, e.g. Haemophilia
4. Patients with risk of developing infective endocarditis or immune compromised patients.
5. Patients with non-vital permanent premolars where root development is already deemed to be completed (i.e. foramen size of 0-1.0mm diameter as determined radiographically).
6. Impacted or horizontally tilted teeth.
7. Concurrent signs of irreversible pathological root resorption determined radiographically, e.g replacement or internal root resorption, which could otherwise affect the prognosis of the tooth.
8. Uncooperative patients, or those unable to cope with treatment under local anaesthesia, rubber dam isolation and taking of intraoral radiographs.

3.4.2 Study settings

3.4.2.1 Recruitment of subjects and consent procedure

(A) Subject recruitment

About 3% of children in Singapore present with dens evaginations on their erupted premolars. The School Dental Service screens children aged 9-10 years (i.e Primary 3 and 4 pupils) for non-vital teeth as a result of fractured dens evaginatus tubercles as part of their annual screening protocols. The majority of potential subjects requiring treatment for non-vital immature permanent teeth will be identified through this screening.

Publicity will be carried out to heighten the awareness of the trial among dentists, and to increase the number of children recruited for the clinical trial. Advertisement emails through the Singapore Dental Association, dental specialist societies, and Oral and Maxillofacial staff at NUH will be distributed.

Treatment will be carried out at the following sites:

1. School Dental Service, Health Promotion board
2. National University Hospital – training and service sites

Clinicians rendering the revascularization procedures will be operators at NUH and School Dental Service, who are trained and already currently treating these cases under similar protocols. Prior to commencement of the study, all operators will be calibrated to the study protocol. All postgraduate student operators will receive standardized instructions and training for the treatment procedures (based on this protocol) at the beginning of their postgraduate course. Their training will be documented in the training and responsibility logs. Should postgraduates be rendering the revascularization procedures as part of their clinical training, they will be supervised at all times by experienced clinical instructors familiar with the treatment protocol.

Students will not be obtaining consent for treatment. Consent for treatment will be obtained by PI or co-investigators only.

(B) Consent procedure

If a patient is deemed suitable for inclusion in this study, parents and patients will be informed of the study by the primary attending dentist, and an Letter of Invitation (**Appendix A**) and information about the study (**Appendix B – Participant Information Sheet with Main ICF**) will be given to potential participants.

Potential subjects will be recruited by a face-to-face contact when they come for their next regular clinic visit. Only the PI and co-investigators will be involved in the consent taking. During the consent taking and consultation appointment, the investigator will counsel the parents/legal guardian and the child on the available treatment options for their condition. He/she will then explain the study to the parents and child.

The consultation session will be conducted in a private consultation room to ensure and protect the privacy of the subject from others' intrusion. The private consultation room will be a safe, closed environment in which the treatment options can be discussed with the parents/legal guardians and the child patient in confidence. The patient will not be recruited if the child declines to participate in the research despite parental consent.

When obtaining consent, the condition of the patient will already be stable and the patient should not be in pain. All emergency procedures would have been conducted in the previous visit, with pain addressed

in the previous session (prior to the recruitment session). Patients would have been given an information sheet about the study, and would hence have some time to read through and consider their options.

The attending dentist of the subject will not be involved in obtaining the consent of their own patient for research, so as to prevent the subject from feeling obliged to join the research, or have a heightened sense of faith and trust in their own physician, and may be more likely to participate. Another dentist who is part of the study team will be tasked to obtain informed consent instead. Possible languages that will be understood by prospective participants are English, Chinese, Malay and Tamil. In the situation that the investigator is unable to speak the language understood by the potential participant, a translator will be involved in helping to translate the information to the potential participant. The translator will be documented in the informed consent form. In this case, the participant will then be required to sign the DSRB short Consent Form (Translated).

Should the parent/legal guardian and child agree to participate in the study, they will be required to sign an Informed Consent form (parents/legal guardians) and assent form (child patient). Once informed consent is obtained, the operator will initiate the treatment.

Informed consent from the parents and child assent will be obtained. **Appendix B (Participant Information Sheet with Main ICF) and Appendix C1-4 (Chinese, Malay, and Tamil Short Consent Form and Child Assent form).**

Participation in this study is purely voluntary. If either parents or patients are unwilling to participate in this study, they will not be recruited. Patients who wish to withdraw from the study may do so at any stage of the study. If the patient declines taking part in this study, the tooth will be accessed and dressed with $\text{Ca}(\text{OH})_2$ according to currently accepted treatment protocol for management of patients with non-vital immature permanent teeth followed by application of MTA and obturation with gutta percha.

The data required will be collected prospectively. All data will be collected and analyzed in a de-identified format, with each individual assigned a unique identification number. IRB approval will be obtained prior to commencement of the study.

3.4.2.2 Intervention workflow (Appendix D)

Initial management of patients in pain:

Dental therapists and officers (who are the first line of clinicians managing emergency cases) will be instructed on the inclusion/exclusion criteria for the study. If a patient is deemed suitable for inclusion in

this study, they will be given an information sheet about the study and registered as a potential participant for the study. The treating clinician will seek the patients' consent to be referred to the study team and obtain their contact details which will be recorded and passed to the study team to schedule a consultation session. The consultation session and treatment will only be carried out by trained and calibrated operators. The estimated waiting period for consultation will be within 1 month of the initial diagnosis/emergency visit.

For patients who are in pain, dental officers will proceed to carry out emergency treatment for the patient, i.e. pulp extirpation/pulpectomy procedures, irrigate only with sodium hypochlorite solution, and seal temporarily with cotton pledge and IRM restorative materials. All procedures will be carried out under local anaesthesia and rubber dam isolation. This procedure is adequate to temporarily relieve the patient from pain. Dental officers will also record the initial pulpal and periapical diagnosis of the tooth involved.

Subsequent visits: Patient contact and consent taking procedures

Potential subjects will be recruited by a face-to-face contact when they come for their next regular clinic visit. During the consent taking and consultation appointment, the operators (investigators/study team) will counsel the parents/legal guardian and the child on the available treatment options for their condition. He/she will then explain the study to the parents and child.

The consultation session will be conducted in a private consultation room to ensure and protect the privacy of the subject from others' intrusion. The patient will not be recruited if the child declines to participate in the research despite parental consent.

When obtaining consent, the condition of the patient will already be stable and the patient should not be in pain. All emergency procedures would have been conducted in the previous visit, with pain addressed in the previous session (prior to the recruitment session). Patients would have been given an information sheet about the study, and would hence have some time to read through and consider their options. The attending dentist of the subject will not be involved in obtaining the consent of their own patient for research, so as to prevent the subject from feeling obliged to join the research, or have a heightened sense of faith and trust in their own physician, and may be more likely to participate.

Should the parent/legal guardian and child agree to participate in the study, they will be required to sign an Informed Consent form (parents/legal guardians) and assent form (child patient). Once informed consent is obtained, the operator will initiate the treatment. The treatment will be carried out over 2 visits, each lasting about 1 hour per session.

For more information on treatment sequence, please see section on Randomization.

First Treatment Visit:

- The tooth will be examined and evaluated for clinical signs of an abscess, increased mobility and presence of the existing coronal seal restoration prior to commencement of local anaesthesia and rubber dam procedures.
- Pre-operative photographs will be taken by the operator. The photographic settings are as follows:
 - Camera: Canon EOS 600D
 - Shutter speed: 1/200
 - F stop: 32
 - ISO: Auto
 - White balance: Auto
- Treatment will be carried out under local anaesthesia and rubber dam isolation. Local anaesthesia with a vasoconstrictor may be used during this step.
- The tooth will be accessed and pulp necrosis will be confirmed. The root canal system will then be irrigated with 1.5% sodium hypochlorite.
- The canal will then be negotiated with minimal or no filing to prevent further weakening of the existing dentinal walls.
- 17% EDTA 10ml will be used to irrigate the canals.
- The canal will then be dried using paper points.
- Control or test procedure will be decided (**Appendix E - Patient ID, Intervention Allocation and Documentation Workflow**)
- The allocated antibiotics will be mixed with sterile water into a grainy mixture.
- The antibiotics will be placed into the root canal with a carrier and pluggers to completely fill the root canal system; Controls will be filled with Ca(OH)_2 , placed in according to currently employed procedures.
- The root canal will then be hermetically sealed with a sterile cotton pledge, IRM and a glass ionomer cement to prevent any coronal leakage or contamination of the root canal with oral microorganisms.
- The patient will then be discharged, and given an appointment to return for the next step of treatment in 4 weeks \pm 7 days.

Second Treatment Visit:

- The tooth will be examined and evaluated for clinical signs of an abscess, increased mobility and presence of the existing coronal seal restoration prior to commencement of local anaesthesia and rubber dam procedures.
 - If any of the above is present, a repeat session of disinfection is necessary and the first treatment visit procedures will be repeated until there is no clinical presence of an abscess or sinus tract. Information on number of additional disinfection visits will be recorded.
 - The operator/assistant will refer to patient ID recorded in treatment notes, and access the Intervention Log and double check the intervention group assigned to the patient prior to preparing the medicament to be used.
- Local anaesthesia without a vasoconstrictor will be administered and the tooth will be isolated and re-accessed as described above.
- The antibiotic mixture will be flushed out of the root canal by irrigation until solution runs clear with sodium hypochlorite. Ca(OH)_2 dressing will be removed by essentially the same procedure.
- The root canal will be irrigated slowly with 10ml 17% EDTA.
- Following this, the root canal will be thoroughly dried with paper points.
- A sterile 23-gauge needle or sterile file with a length of 25mm will be inserted beyond the working length and past the confines of the root canal into the periapical tissues to intentionally induce bleeding into the root canal. The bleeding is then allowed to fill the root canal.
- Once the root canal is filled with blood, a moist cotton pledge will be placed in the root canal below the cementoenamel junction (CEJ), and a clot will be allowed to form in the root canal.
- Once the clot is formed, the coronal portion of the root canal will be cleaned (with a new sterile cotton pledge moistened with saline) to remove any remnants of blood, which could cause discolouration in future
- Collagen will be placed directly onto the blood clot.
- The access cavity will be hermetically sealed with three layers of materials: Biodentine®, glass ionomer cement (Fuji IX) and composite resin. A post-op X-ray will be taken.
- Patients will then be reviewed at 3 months (\pm 2 weeks), 6months (\pm 2 weeks), 9months (\pm 2 weeks), 12 (\pm 2 weeks) months, 15 (\pm 2 weeks) months and 18 (\pm 2 weeks) months from treatment completion date. It would be acceptable for patient to miss one or more recall visits if patient comes for last recall visit at 18(\pm 2 weeks) months post treatment.

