4.2. Allocation concealment and implementation

Randomization codes will be held by the delegated study team member, who will convey the randomization allocation to the operator. The delegated study team member (randomization code holder) will be responsible for maintaining the allocation log, and will inform the investigator of the assigned randomization ID as well as the intervention group assigned to the patient. (**Appendix E - Patient ID and Intervention Allocation and Log Documentation Workflow**). The study team member who will perform the randomization will be trained and will be delegated in the responsibility log.

Materials to be used in both groups will be made available at each recruitment site. Potential participants must firstly be assessed for eligibility, be recruited and consented, after which only can the randomization codes be accessed.

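### The repeat-disinfection rule at the second treatment visit contradicts itself: it counts an intact coronal seal as a reason to repeat, and its start and stop conditions do not match

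*Protocol*

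**What the plan says.** All of the following is in protocol section 3.4.2.2 unless stated otherwise.

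- **End of the first treatment visit.** The medicated canal is closed: "The root canal will then be hermetically sealed with a sterile cotton pledge, IRM and a glass ionomer cement". The patient returns after 4 weeks ± 7 days.
- **Examination at the second visit.** The tooth is evaluated for "clinical signs of an abscess, increased mobility and presence of the existing coronal seal restoration".
- **Start of a repeat.** "If any of the above is present, a repeat session of disinfection is necessary".
- **End of the repeats.** "the first treatment visit procedures will be repeated until there is no clinical presence of an abscess or sinus tract".
- **Recording.** The number of additional disinfection visits is recorded. The sentence does not mention the reason.
- **Who knows the arm.** Under section 4.2 the holder of the randomisation codes "will inform the investigator of the assigned randomization ID as well as the intervention group assigned to the patient", and the allocation is passed to the operator. Section 4.3 lists only participants and outcome assessors as blinded. Directly after the repeat rule, the operator or assistant is told to check the assigned group in the log before preparing the medicament.
- **Where it is applied.** Section 3.4.2.1 names two treatment settings, with operators who may include supervised postgraduates.

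**The concern.** The rule is operative text, not background. Repeating the first-visit procedures means placing the allocated dressing again, so the rule decides how many courses of the randomised medicament a tooth receives. If its wording cannot be followed consistently, operators have to settle for themselves which teeth are re-dressed and when to stop.

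These operators know the arm and work at two sites. Differences in how they resolve the wording could lead to different numbers of courses by arm or by site, for reasons unrelated to what the medicament does. Reviews are timed from treatment completion, while root growth is measured from the pre-operative radiograph. A repeat therefore also lengthens the interval over which growth accrues for that tooth. Change in root length is the outcome on which section 3.5 bases the sample size.

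**Working it through.** The plan gives no figure to reproduce here. The check compares the two conditions and then does some simple arithmetic on time.

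**Start and stop conditions side by side**

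| Finding | Starts a repeat? | Tested by the stop condition? |
|---|---|---|
| Signs of an abscess | Yes | Yes |
| Increased mobility | Yes | No |
| Coronal seal present | Yes, as worded | No |
| Coronal seal lost | No, as worded | No |
| Sinus tract | Not named, unless taken as a sign of an abscess | Yes |

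Only abscess appears on both sides. Taking each finding alone:

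1. *Seal intact, nothing else.* A repeat is called for, although the stop condition is already met. This is the state that the first visit is meant to produce.
2. *Seal lost, nothing else.* No repeat is called for.
3. *Mobility only.* A repeat is called for. If mobility persists on return, the same examination calls for another repeat, while the stop condition says that repeats are over.
4. *Sinus tract only.* It can prolong repeats, but whether it can start them depends on how the operator reads the abscess item.

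If the seal item is read charitably as loss of the seal, cases 1 and 2 change places, but the stop condition still does not test the seal. Cases 3 and 4 are unaffected.

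**Time added by one repeat**

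- The interval after a dressing is 28 ± 7 days, so one repeat adds 28 − 7 = 21 to 28 + 7 = 35 days, or 3 to 5 weeks.
- From the pre-operative radiograph to the final review, a two-visit course takes about 1 + 18 = 19 months. One repeat adds about 1 month: 1 / 19 = 5.3% for that tooth.

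**What this could mean between arms**

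Let *d* be the difference between arms in the proportion of teeth with one repeat. The shift in mean observation time is *d* × 1/19. The documents give no value for *d*, so these are assumptions:

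| *d* (assumed) | Shift in mean observation time |
|---|---|
| 0.10 | 0.10 / 19 = 0.5% |
| 0.20 | 0.20 / 19 = 1.1% |
| 0.40 | 0.40 / 19 = 2.1% |

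For comparison, the 18-month review window of ± 2 weeks is already 4 weeks wide, about the length of one repeat. This arithmetic covers time only. The documents give nothing from which to quantify the effect of a further course of dressing itself.

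**The case against.** Several points on the other side are sound.

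- **The seal wording is very likely a slip.** The same list appears at the first visit as a plain examination checklist, the canal is deliberately sealed, and operators are trained and calibrated. A reader might infer that all 60 teeth would be re-treated. That is what the literal words yield, but the surrounding text shows that it was not intended, and it is not a realistic size for the problem.
- **The visit count is not a contradiction.** A reader might set "The treatment will be carried out over 2 visits" against the repeat rule. Section 3.1, however, defines the therapy as "at least a two-stage procedure", and section 3.4.2.2 provides for additional visits and counts them. Two visits is the planned course, with a written exception.
- **Start and stop lists may legitimately differ.** A sign can prompt one further session without having to resolve before treatment proceeds. The difference alone is no error, and it does not follow that the lists must be identical. What stands is that the text does not say whether this is meant, and persisting mobility receives two opposite instructions.
- **There is some mitigation.** The number of repeats is recorded, so an imbalance could be seen, and section 6.2 plans an intention-to-treat analysis. The workflow in Appendix D and the data sheet in Appendix F are not shown and may be clearer. Even so, the protocol body would still conflict with itself.

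**Conclusion.** The point holds as an internal contradiction in the repeat-disinfection rule, and it should be corrected. The mismatch over mobility, and the doubt over sinus tract, remain even when the seal wording is read charitably. Nothing else in the protocol text resolves them.

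For a re-treated tooth, each repeat means one more course of the allocated dressing, about 3 to 5 weeks, and roughly 5% more observation time. A reader might take that 5% as a bias in the treatment comparison. It is not: it applies to a single tooth, and a bias would require repeat rates to differ by arm because of the wording. Under the assumed differences of 10 to 40 percentage points, the shift in mean observation time is about 0.5% to 2%. The documents contain no evidence that repeats would differ by arm; they only leave room for it, because the people applying the rule are unblinded. Any between-arm effect is therefore likely to be small, with the reservation that the effect of an extra course itself cannot be sized from the documents.

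**What to change.** 1. The sponsor's clinicians reconcile the start and stop statements in section 3.4.2.2, so that an operator can tell from the text which findings lead to a repeat and when repeats end. Which findings these are, and whether the two lists should coincide, is for them to decide.
2. Correct the coronal-seal wording so that it says what is meant, and check that Appendix D agrees.
3. Record the reason for each repeat next to the number already recorded, if the data sheet does not already do so.
4. Summarise the number of repeats and their reasons by arm. If the statistical analysis plan already provides for this, nothing further is needed.

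The cost is a wording change in the protocol, one field on the data sheet and one descriptive table. No additional visit, procedure or radiograph is involved, and the sample size is unaffected.
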